9.2.6.4. Vital Signs

Supine blood pressure and pulse/heart rate measurements should be preceded by at least 5 minutes of rest in a quiet setting without distractions (eg, television, cell phones).

The following measurements will be performed:

- Heart rate (beats per minutes, bpm), respiratory rate (breaths per minute), systolic blood pressure (mmHg) and diastolic blood pressure (mmHg)
- Body temperature (tympanic or oral route)

Confirmatory vital signs measurement can be performed if inconsistent with a prior measurement. If any clinically significant changes in vital signs are noted, they will be reported as AEs and followed to resolution, or until reaching a clinically stable endpoint.

9.2.6.5. Physical Examination

A full physical examination will be carried out within 56 days of vaccination, on admission to the Unit, and on discharge from the Unit. At all other visits, an abbreviated, symptom-directed examination will be performed by the investigator based on any clinically relevant issues, clinically relevant symptoms and medical history. Symptom-directed physical examination may be repeated if deemed necessary by the investigator.

Physical examinations will be performed by the investigator or appropriately trained delegate. Any abnormalities or changes in severity noted during the review of body systems should be documented in the eCRF.

10. SUBJECT COMPLETION/DISCONTINUATION OF STUDY VACCINE/ WITHDRAWAL FROM THE STUDY

10.1. Completion

A subject will be considered to have completed the study challenge if he or she has been challenged in the quarantine Unit and remained until meeting the requirements for discharge from the Unit. A subject will be considered to have completed the study if he or she has completed assessments at the final visit at 6 months post-vaccination.

10.2. Discontinuation from Challenge Phase/Withdrawal from the Study

Discontinuation from Challenge Phase

Subjects will be discontinued prior to the viral challenge phase (ie, pre-inoculation) for the reasons listed below. These subjects must not receive the viral challenge but should continue other study procedures, eg, safety follow-up:

- Pregnancy
- Any SAE
- Any related AE, worsening of health status or intercurrent illness that, in the opinion of the investigator, precludes the subject from viral challenge
- The randomization code is broken by the investigator or the study-site personnel

Overflow subjects from the first cohort will be challenged in subsequent cohorts. Any subject who is vaccinated in subsequent cohorts but not challenged will be followed to the end of the study.

Withdrawal from the Study

Each subject has the right to withdraw from the study at any time for any reason without affecting the right to treatment by the investigator. Although the subject is not obliged to give a reason for withdrawing prematurely, the investigator should make a reasonable effort to ascertain the reason(s) while fully respecting the subject's rights.

A subject will be withdrawn from the study for any of the following reasons:

- Repeated failure to comply with protocol requirements
- Decision by the sponsor or the investigator to stop or cancel the study
- Decision by local regulatory authorities and Institutional Review Board/Independent Ethics Committee (IRB/IEC) to stop or cancel the study
- Lost to follow-up
- Withdrawal of consent

- Death

Any unnecessary study discontinuation should be avoided. Should a subject be withdrawn, all efforts should be made to complete and report the observations as thoroughly as possible. Whenever a subject is withdrawn from the study, independent of the reason, a final evaluation should be completed for that subject and the major reason for which the subject was withdrawn must be stated. If a subject is lost to follow-up, every reasonable effort must be made by the study-site personnel to contact the subject and determine the reason for withdrawal. The measures taken to follow-up must be documented.

When a subject withdraws before completing the study, the reason for withdrawal is to be documented in the eCRF and in the source document. Study vaccine assigned to the withdrawn subject may not be assigned to another subject. In general, subjects who withdraw will not be replaced, unless that subject was randomized but did not receive any study vaccine. Any subject who withdraws from the study after vaccination but before challenge will be replaced in the challenge by an overflow subject.

For those subjects who are unable to continue participation in the study, but for whom consent is not withdrawn, an exit visit will be conducted as soon as possible (see Section 9.1.8).

Subjects who wish to withdraw consent from participation in the study will be offered a single exit visit for safety follow-up (prior to formal withdrawal of consent). They have the right to refuse.

Precautions for any subject leaving the challenge Unit are listed in Section 4.3.

Withdrawal from the Use of Samples in Future Research

The subject may withdraw consent for use of samples for future research (refer to Section 16.2.5). In such a case, samples will be destroyed after they are no longer needed for the clinical study. Details of the sample retention for research are presented in the main ICF.

10.3. Contraindications to Vaccination

The following events constitute a contraindication to vaccination at that point in time. If any of these events occur at the scheduled time for vaccination, the subject may be re-screened (if vaccination number not assigned), or withdrawn at the discretion of the investigator and after consultation with the sponsor. *Note:* the minimum time between vaccination and challenge is 24 days:

- Severe acute illness at the time of vaccination. This does not include minor illnesses such as diarrhea.
- Fever (body temperature ≥ 37.8 °C) at the time of vaccination.

Note: medically indicated vaccines should be given at least 14 days before or 14 days after study vaccine administration and the viral challenge (see Section 4.3).

11. STATISTICAL METHODS

Statistical analysis will be done by the sponsor or under the authority of the sponsor. A general description of the statistical methods to be used to analyze the immunogenicity and safety data is outlined below. Specific details will be provided in the SAP.

Planned analyses are described in Section 11.8.

11.1. Analysis Sets

The **Full Analysis (FA) Set** includes all subjects who were randomized and received study vaccine, regardless of the occurrence of protocol deviations. Vaccination assignment will follow the as-treated principle. All safety and subject information analyses will be based on the FA set. As a sensitivity analysis, key immunogenicity tables will also be based on the FA set.

The **Intent-to-Treat-Challenge (ITTc)** population is a subset of the FA set that includes all randomized, vaccinated and challenged subjects. All efficacy analyses will be performed on the ITTc population. Important subject information tables might be repeated based on the ITTc population as well.

The **Per-protocol Immunogenicity (PPI) Set** will include all randomized and vaccinated subjects for whom immunogenicity data are available, excluding subjects with major protocol deviations expecting to impact the immunogenicity outcomes.

In addition, for subjects who experience a natural RSV infection (based on RT-PCR, or other sources), samples taken after the natural infection will not be included in the PPI set.

The analysis of immunogenicity will be based on the PPI set.

11.2. Sample Size Determination

[figure not shown]
A sample size of 44 challenged subjects (22 vaccinated and 22 placebo subjects) was chosen as this would provide sufficient evidence to assess if the challenge model is a reasonable approach to examine vaccine efficacy. A multiple of 22 subjects was selected given the capacity of the quarantine Unit.

The sample size was based on the ability to detect trends with a high one-sided alpha (20%), given this is an exploratory study whose partial aim is to determine the utility of the RSV human challenge model for RSV vaccine development. Figure 2 shows the expected power for several reductions in VL-AUC of the quantitative RT-PCR assay, with this selected sample size, a mean VL-AUC in the placebo group of 320 log₁₀ h/mL with corresponding standard deviation 275, an infection rate in placebo of 65% and a one-sided alpha of 5% and 20% based on a Wilcoxon Rank Sum test. This graph suggests that for a one-sided alpha level of 20%, the study has at least 80% power if Ad26.RSV.preF induces a reduction of VL-AUC of the quantitative RT-PCR assay by 50% or more. For a one-sided alpha level of 5%, the study has at least 80% power if Ad26.RSV.preF induces a reduction of VL-AUC of the quantitative RT-PCR assay by 75% or more.

An effect that is significant at 5% (one-sided) will be considered a significant effect. An effect that is significant at 20% (one-sided) will be considered as a trend. This trend, if observed, might be confirmed in future studies.

As this is an exploratory study, the statistical assumptions described above will need to be demonstrated to be correct for the analysis to be conducted as indicated below and as planned in further detail in the SAP. For example, if the infection rate from the study is considerably below 65% then the study will be considered to be underpowered to be able to accurately determine the stated aims. The infection rate in the placebo group will be followed on an ongoing basis by an unblinded individual who does not have any other study function to ensure a sufficient infection rate has occurred. If the infection rate is lower than anticipated, additional subjects may be enrolled, initially four additional subjects in each arm and up to 70 in total. This is to ensure that a high enough number of evaluable subjects is reached in each arm.

Figure 2: Expected Power for Several Reductions in Viral Load

11.3. Subject Information

For all subjects, demographic characteristics (eg, age, height, weight, body mass index [BMI], race, and gender), and other baseline characteristics (eg, physical examination, medical history, and concomitant diseases) will be tabulated and summarized with descriptive statistics.

11.4. Efficacy Analyses

For efficacy, baseline is defined as the last assessment challenge with the virus.

The **primary efficacy endpoint** is the VL-AUC of RSV-A Memphis 37b as determined by quantitative RT-PCR assay of nasal wash samples. The VL-AUC is calculated based on the viral load values measured twice daily, starting with the baseline value, and ending with the last available value before discharge.

For this primary efficacy endpoint the exact Wilcoxon Rank Sum test will be performed and the one-sided p-value will be interpreted at the 5% and 20% significance level, specifically only analysing the statistical significance of a reduction in VL-AUC in the active versus placebo groups.

The **secondary efficacy endpoints** are:

- The peak viral load of RSV-A Memphis 37b, defined as the maximum viral load as determined by quantitative RT-PCR assay of nasal wash samples, observed over the entire time period
- The effect of vaccination on viral load and symptoms on Day 6 and Day 7
- The viral load of RSV-A Memphis 37b as determined by quantitative RT-PCR assay of nasal wash samples over time
- The VL-AUC of RSV-A Memphis 37b as determined by quantitative culture of RSV of nasal wash samples and the corresponding AUC
- Weight of mucus produced over time and the corresponding AUC, tissue count
- Proportion of subjects with symptomatic RSV infection. Symptomatic RSV infection is defined in two ways:
 - Conservative: the subject has two or more quantifiable RT-PCR measurements on different samples **and** the subject has one of the following
 - symptoms from two different categories (Upper Respiratory, Lower Respiratory, Systemic) from the SSC, regardless of grade and assessment timepoint.
 - any Grade 2 symptom from any category.
 - Liberal: two or more quantifiable RT-PCR measurements plus any clinical symptom of any severity.

Note: the quantifiable RT-PCR assessment and the symptoms should not necessarily occur at the same day.

Exploratory efficacy endpoints are:

- Proportion of subjects with symptomatic RSV infection (RT-PCR or serology). Symptomatic RSV infection is defined as having two or more quantifiable RT-PCR measurements or serology confirmation of RSV, and any clinical symptom of any severity.
- Total clinical symptom score (using a composite of 10 and 13 self-reported symptoms on the SSC) over time and the corresponding AUC.

- To determine the most effective efficacy endpoint, additional exploratory efficacy endpoints will be described in the SAP.

Continuous variables will be summarized with descriptive statistics of the actual values and the changes from baseline where appropriate. For categorical variables, frequency tables will be presented. Difference in proportions and corresponding confidence intervals (CIs) may be calculated where appropriate.

The relation between viral load and clinical symptoms will be graphically explored.

Spirometry

Descriptive statistics of values and changes from baseline for FEV₁, FVC, and FEV₁/FVC will be summarized at each scheduled timepoint. The percentage of subjects with values beyond clinically important limits will be summarized.

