9.2.5. Respiratory Parameters: Spirometry

Spirometry (FEV₁, FVC, FEV₁/FVC) will be performed at several timepoints as specified in the [Time and Events Schedule](#). Spirometry may also be investigated at any time following respiratory signs or symptoms (repeated coughing, bradypnea, tachypnea, rales and rhonchi) of respiratory difficulties. Spirometry will be performed as per hVIVO's Operating Instruction. In case of respiratory difficulties, the investigator may decide to perform additional lung function testing.

Spirometry will be done for each subject at approximately the same timepoint on each day from Day 0.

At each timepoint, three technically acceptable measurements will be recorded using a spirometer. The best reading from each assessment (as provided by the spirometry machine) will be used for analysis.

The following data will be automatically calculated:

- FEV₁ % predicted;
- FEV₁/FVC ratio (absolute, not predicted);

Any clinically relevant changes in pulmonary function occurring during the study will be recorded on the Adverse Event Section of the eCRF.

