3. GENERAL ANALYSIS DEFINITIONS

3.1. Study phases

The baseline (or reference) value for safety and immunogenicity analysis will be defined as the value of the last available assessment prior to vaccination (Day -28). For ECG values the baseline (or reference) value will be defined as the value of the last available assessment prior to challenge on Day 0, since ECGs for safety assessment are performed only during the challenge period.

The baseline (or reference) value for the efficacy analysis will be defined as the value of the last available assessment prior to challenge on Day 0.

The safety analysis will present all results by period, based on the phase definition in Section [3.1.1](#).

The immunogenicity analysis will summarize all results in the following immunogenicity timepoints:

- Baseline (vaccination)
- 28 days post-vaccination*
- 28 days post-challenge

*Includes all assessments taken between 22 and 33 days after vaccination.

In case there are subjects for which samples were taken later than 33 days after vaccination, the results will appear in listings.

Moreover,

$$\text{Study Day} = \text{visit date} - \text{date of Vaccination}$$

Listings will be shown per phase and time point.

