6.2.1. Secondary and Exploratory Efficacy Endpoint Analysis

For viral loads of RSV-A Memphis 37b as determined by quantitative RT-PCR assay and by quantitative culture of RSV, number of observations, mean, standard error, median, first and third interquartile will be tabulated and means with standard errors will also be graphically presented per time point.

For clinical symptoms scores, total clinical symptom scores, mucus weight and number of tissues, number of observations, mean, standard error, median, first and third interquartile will be tabulated and means with standard errors will also be graphically presented per time point.

For peak viral load based on the quantitative RT-PCR assay, number of observations, mean, standard error, median, first and third interquartile will be tabulated for both groups and graphically presented with boxplots. Exact Wilcoxon Rank Sum tests will also be performed to compare the mean in the active versus placebo groups and the corresponding p-values will be presented. Note the study is only powered for the primary efficacy endpoint and not for any of the secondary one, interpreting these p-values should be done with caution.

For AUCs of viral loads, clinical symptoms and mucus weight, number of observations, mean, median, first and third interquartile (q1, q3) will be calculated for both groups and graphically presented with boxplots. Exact Wilcoxon Rank Sum tests will also be performed to compare AUCs in the active versus placebo groups and the corresponding p-values will be presented. Note the study is only powered for the primary efficacy endpoint and not for any of the secondary one, interpreting these p-values should be done with caution.

Descriptive statistics (number of observations, mean, standard errors, median, q1, q3) of values and changes from baseline for FEV₁, FVC, and FEV₁/FVC will be summarized at each scheduled timepoint. Mean with standard errors of actual values and changes from baseline will also be graphically presented. Finally, spirometry values that are below the clinically important limits, provided in the table below, will be classified as ‘abnormally low’ and the percentage of subjects with ‘abnormally low’ values will be summarized.

Parameter	Clinically Important Limits
FEV ₁	80%
FVC	80%
FEV ₁ /FVC	70%

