7.2. Clinical Laboratory Tests

For laboratory safety parameters, only abnormalities emerging will be tabulated by worst abnormality grade using the FDA table in [Attachment 1](#). Blood and urine for laboratory safety assessments will be collected within 56 days of vaccination, pre-vaccination, at 7 days post vaccination, prior to challenge on Day -1 or Day -2, post challenge at day 12 and Day 28. Moreover, blood for assessment of cardiac enzymes will also be collected on Days 3, 7, and 11.

An abnormality (toxicity grade or abnormality based on normal ranges) will be considered as emerging in a particular period if it is worse than the baseline value. If the baseline is missing, the abnormality is always considered emerging. A shift from ‘abnormally low’ at baseline to ‘abnormally high’ post baseline (or vice versa) is also emerging. In case a laboratory test result is censored (no numeric value is available, but only a verbatim term) then a numeric value will be imputed by a value exceeding the cut-off value with one unit. (<x: subtract 1 unit from x, >x: add 1 unit to x; <3.45 is imputed with 3.44).

In case no toxicity grades are defined for a test, the abnormalities (above/below normal range) will be used. In determining toxicity grades, the following rules are applied:

- worst grades/abnormalities are determined over the whole observational period for each trial period separately, including all post-baseline measurements of that period.
- The abnormalities ‘abnormally low’ and ‘abnormally high’ are considered equally important, i.e. if a subject has as well an abnormally low as an abnormally high value post-baseline, both abnormalities are shown in the tables. (This means that the sum of the percentages can be more than 100%)
- Note: as the grading scale for some parameters in the grading table has some gaps (zones where no toxicity grade definition exists), laboratory results falling in these zones will be allocated to the adjacent worst-case grade.
- If a laboratory value falls within the grading as specified in the grading table but also within the local lab normal limits, the value is considered as normal.
- HGB: for hemoglobin grades are based on both actual values and changes. Those grading will be listed separately. In addition, for the grading on the changes of HGB, the corresponding actual value should be at least grade 1.

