7.3. Vital Signs and Physical Examination Findings

Similar to laboratory tests, only vital signs abnormalities emerging after vaccination and after challenge will be tabulated by worst abnormality grade.

Heart rate (beats per minutes, bpm), respiratory rate (breaths per minute), systolic blood pressure (mmHg) and diastolic blood pressure (mmHg) will be collected. The respective vital signs abnormalities are defined in Table 4. Moreover, only the vital signs values will be used, no clinical interpretations, therefore, grade 3 and 4 is shown combined as grade 4 always requires clinical interpretation.

Table 4: Vital Signs Toxicity

Vital Signs	Grade 1	Grade 2	Grade 3/4
Tachycardia – beats (HR) per minute	101 – 115	116 – 130	>130
Bradycardia – beats (HR) per minute	50 – 54	45 – 49	< 45
Hypertension (systolic) - mm Hg	141 – 150	151 – 155	>155
Hypertension (diastolic) - mm Hg	91 – 95	96 – 100	>100
Hypotension (systolic) - mm Hg	85 – 89	80 – 84	< 80
Respiratory Rate - breaths per minute	17-20	21-25	>25

Temperature from diary and on-site assessments from day of vaccination will be allocated to predefined temperature intervals (from 37.5° C until 40°C, in steps of half degree increments; eg <37.5, 37.5-<38, 38-<38.5, ... >40). A table will be created, showing the maximum temperature for both diary and onsite assessments combined.

A listing of temperatures from Day -2 or -1 will also be provided.

Temperature collected during the post challenge period will be summarized descriptively over each timepoint.

Finally, a listing of subjects with fever according to the FDA grading table, across the entire study period, will be provided.

Any abnormal physical examination result will be documented as AEs, by the investigator.

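### The spirometry abnormality percentage has no baseline condition and no time window, so subjects already below a limit before challenge are counted as abnormal

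*Protocol*

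**What the plan says.** Protocol 11.4 (Spirometry) plans descriptive statistics of values and changes from baseline, and then adds: "The percentage of subjects with values beyond clinically important limits will be summarized". SAP 6.2.1 makes this operational with a rule that reads in part: "spirometry values that are below the clinically important limits, provided in the table below, will be classified as". The label it gives them is abnormally low, and the share of subjects who have such a value is then reported. The limits are 80% for FEV1, 80% for FVC and 70% for FEV1/FVC. No condition on the pre-challenge value is given, and no window of assessments.

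The same SAP section also plans descriptive statistics "of values and changes from baseline for FEV₁, FVC, and FEV₁/FVC will be summarized at each scheduled timepoint", with graphs of the means. A suitable baseline exists, because SAP 3.1 says that the "value for the efficacy analysis will be defined as the value of the last available assessment prior to challenge on Day 0". Spirometry is done at screening and on entry to the Unit (Protocol 9.1.3 and 9.1.5.1).

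Elsewhere the SAP ties abnormalities to baseline:

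- Laboratory (SAP 7.2): an abnormality "will be considered as emerging in a particular period if it is worse than the baseline value".
- Vital signs (SAP 7.3): "only vital signs abnormalities emerging after vaccination and after challenge will be tabulated by worst abnormality grade".
- ECG (SAP 7.4): worst emergent abnormalities are analysed, alongside classification of the actual values.

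On units, Protocol 9.2.5 lists two automatically calculated quantities: FEV1 as % predicted, and the FEV1/FVC "ratio (absolute, not predicted"). SAP 6.2 lists FVC in (%) without saying of what.

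**The concern.** A percentage of subjects below a limit is meant to show who developed an important loss of lung function. As written, it also counts anyone who was below the limit before the virus was given. Such subjects can be enrolled. Spirometry is among the screening evaluations, but Protocol 4.1 to 4.3 set no spirometry cut-off. The challenge exclusion for abnormal findings names only ECG and vital signs. Childhood asthma is accepted if the subject is asymptomatic without treatment.

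One of the exploratory objectives is a trend for efficacy on spirometry. With 22 challenged subjects per arm, one pre-existing low value moves an arm by 1/22 = 4.5 percentage points. A few such subjects could imitate or hide a difference. With no window stated, two programmers could also produce different percentages from the same data: per timepoint or at any time, with or without the admission value.

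**Working it through.** The documents give no expected spirometry rate, so there is no planned figure to reproduce. The inputs are:

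- 22 challenged subjects per arm (Protocol 11.2), randomized 1:1 within cohort (Protocol 5).
- b, the share of subjects below a limit before challenge: not in the documents, so assumed.
- e, the share of the remaining subjects who newly fall below it after challenge: not in the documents, so assumed.

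**Plausible range for b.** If % predicted is normal with mean 100 and SD 10, 12 or 15 (assumed), the probability of a value below 80 is 2.3%, 4.8% or 9.1%. That is about 0.5 to 2 subjects per arm of 22.

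**Dilution.** If baseline-low subjects stay low, the rate as written is b + (1 − b)e. With equal b in both arms, the expected difference between arms is (1 − b)(e_placebo − e_vaccine). For an assumed e of 30% on placebo and 10% on vaccine:

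| b | placebo | vaccine | difference (points) |
|---|---|---|---|
| 0% | 30.0% | 10.0% | 20.0 |
| 5% | 33.5% | 14.5% | 19.0 |
| 9% | 36.3% | 18.1% | 18.2 |
| 15% | 40.5% | 23.5% | 17.0 |

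Among subjects at or above the limit at baseline, the rate is e itself, so the difference stays at 20 points whatever b is.

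**Share of flagged subjects who were already low**, b / (b + (1 − b)e):

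| b | e = 2% | e = 10% | e = 20% |
|---|---|---|---|
| 2.3% | 54% | 19% | 11% |
| 5% | 72% | 34% | 21% |
| 9% | 83% | 50% | 33% |

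Baseline-low subjects are the majority only when e < b/(1 − b). For b = 5% that means e below 0.05/0.95 = 5.3%.

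**Chance imbalance.** Take the baseline-low counts in the two arms as independent Binomial(22, b). The probability that they differ by two or more, which is 2/22 = 9 percentage points, is:

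| b | P(difference ≥ 2) |
|---|---|
| 3% | 16% |
| 5% | 28% |
| 8% | 39% |

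At b = 5%, the probability that at least one of 44 subjects is low at baseline is 1 − 0.95^44 = 0.90.

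**FVC.** Set side by side, Protocol 9.2.5 gives FEV1 as % predicted and the ratio as absolute, and has no percentage for FVC. The SAP applies an 80% limit to FVC (%). The reference for that percentage is not defined in either place.

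**The case against.** The best defence is that within-subject change is already analysed. Changes from baseline are summarized and plotted for all three parameters, and Protocol 9.2.5 sends clinically relevant changes in pulmonary function to the adverse event pages. This stands and keeps the matter minor. It does not repair the percentage, because a mean change can conceal a few subjects who newly cross a limit.

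The population also makes a low baseline less likely. Subjects must be in good health, and Protocol 4.2 excludes illness, including significant pulmonary illness, that could confound the assessments. That reduces b but does not set it to zero.

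The emergent rules cited for comparison sit in the SAP's safety section, while spirometry is an efficacy endpoint. The symptomatic-infection endpoints have no emergence condition either. The comparison therefore shows that the SAP has a ready convention, not that it breaks a rule of its own. A table by timepoint with an admission column would show the baseline percentage, but the text does not promise one for this rate, and marginal percentages would not show who crossed.

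An emergent flag is not perfect. Suppose there is no challenge effect, mean FEV1 is 98 to 102% predicted, the between-subject SD is 10 to 12 and the day-to-day SD is 2 to 3.5 points (all assumed). Simulation then still marks 2% to 8% of subjects as newly low at some time over 12 days, against 3% to 16% under the rule as written.

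Three stronger readings are tempting, and the documents do not support them:

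- That the rate mainly measures who was enrolled. This needs new abnormality to be rarer than baseline abnormality. That is plausible, since Protocol 1.2 describes mild, mainly upper respiratory illness, but it is not shown.
- That the comparison is biased. Allocation is randomized, so what remains is dilution and chance imbalance.
- That FVC % predicted will be unavailable. The SAP names FVC in (%), so the gap is an undefined percentage and a missing list entry.

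**Conclusion.** The point holds as a minor one. The percentage beyond the "clinically important limits" has no baseline condition and no window, and nothing in the eligibility criteria prevents a low starting value. The effect is a somewhat smaller contrast (19 to 17 points in place of 20 for a baseline-low rate of 5% to 15%, in the example) and chance imbalance (about 16% to 39% probability of a 9-point or larger difference for 3% to 8%). These sizes rest on assumed baseline-low and new-abnormality rates, and on baseline-low subjects staying low. The endpoint is exploratory and descriptive, with no test planned for this percentage, and the primary analysis is untouched.

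**What to change.** In SAP 6.2.1, with matching words in Protocol 11.4, report by arm:

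- the percentage of subjects below each limit at the last pre-challenge assessment;
- the emergent post-challenge percentage: at or above the limit before challenge and below it after, with subjects at or above the limit at baseline as the denominator, per timepoint and at any time from challenge to discharge;
- a shift table from baseline to worst post-challenge category.

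As a minor alignment, state in the SAP that FVC (%) is % predicted, and add it to the calculated values in Protocol 9.2.5.

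The cost is a few sentences, one derived flag and one table. The admission spirometry is already collected, so there are no new visits, procedures or subjects.
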